11.2.5 Safety Analyses

The safety analyses will be performed using the safety population (all patients who have received at least one dose of lucitanib).

11.2.5.1 Extent of Exposure

The following will be summarized by individual dose group and by dose group combined:

- Number of cycles initiated
- Number of dose reductions, or interruptions

The number of cycles initiated will be investigated by summarizing the number of cycles started by each patient. The number of patients with at least one dose reduction/delay or interruption will be summarized with frequencies and percentages.

11.2.5.2 Adverse Events

AE coding will be performed using the Medical Dictionary for Drug Regulatory Activities. The severity of the toxicities will be graded according to the NCI CTCAE Version 4.03 criteria whenever possible. Treatment-emergent AEs are defined as AEs with an onset date on or after the date of first dose of lucitanib until the date of the last dose of protocol-specified treatment plus 28 days. AEs will be considered treatment-emergent if all or part of the date of onset of the AE is missing and it cannot be determined if the AE meets the definition for treatment-emergent.

The number and percentage of patients who experienced treatment-emergent AEs for each system organ class and preferred term will be presented by individual dose group and by dose groups combined. Multiple instances of the treatment-emergent AEs in each system organ class and multiple occurrences of the same preferred term are counted only once per patient. The number and percentage of patients with at least one treatment-emergent AE will also be summarized by individual dose group and by dose groups combined.

Separate tables will present the following by cohort:

- All treatment-emergent AEs
- Treatment-emergent AEs by CTCAE Version 4.03 grade
- Grade 3 or greater treatment-emergent AEs
- Treatment-related, treatment-emergent AEs
- Serious treatment-emergent AEs
- Serious treatment-related AEs
- Treatment-emergent AEs with an outcome of death
- Treatment-emergent AEs leading to discontinuation of lucitanib
- Treatment-emergent AEs resulting in interruption, reduction, or delay of lucitanib

The incidence of treatment-emergent AEs will be summarized by relationship to lucitanib using “treatment-related” and “not treatment-related” categories. If a patient experiences multiple occurrences of the same AE with different relationship categories, the patient will be counted once as a relationship category of treatment-related.

If a patient experiences multiple occurrences of the same AE with different intensity toxicity grades, the patient will be counted once for the maximum (most severe) toxicity grade. AEs with a missing intensity will be presented in the summary table with a toxicity grade of “Missing.” For each toxicity grade, the number and percentage of patients with at least one treatment-emergent AE of the given grade will be summarized.

Non-treatment-emergent AEs (pre-treatment and post-treatment) will be presented in the data listings.

11.2.5.3 Clinical Laboratory Evaluations

Clinical laboratory evaluations include the continuous variables for hematology, serum chemistry, and urinalysis. Laboratory values will be presented in Systeme International units. The baseline laboratory value will be defined as the last value prior to or on the day of the first dose of lucitanib. The on-treatment period will be defined as the day after the first dose of lucitanib to 28 days after the last dose of lucitanib. Laboratory values collected during the on-treatment period will be included in the summary tables. The laboratory values collected after the on-treatment period will only be presented in the data listings.

The summary of laboratory data will include descriptive statistics (N, mean, standard deviation, median, minimum, and maximum) of the maximum, minimum, and last value during the on-treatment period by dose group. Summaries using descriptive statistics of the change from baseline to the maximum, minimum, and last value during the on-treatment period will also be given by dose group. Separate listings will be produced for clinically significant laboratory abnormalities (i.e., those that meet Grade 3 or 4 criteria according to CTCAE Version 4.03) by individual dose group and by dose groups combined.

11.2.5.4 Vital Signs Measurements

The baseline vital signs measurement will be defined as the last value prior to or on the day of the first dose of lucitanib. The on-treatment period will be defined as the day after the first dose of lucitanib to 28 days after the last dose of protocol-specified treatment. Vital signs measurements collected during the on-treatment period will be included in the summary tables. The vital signs measurements collected after the on-treatment period will only be presented in the data listings.

The summary of vital signs data will include descriptive statistics (N, mean, standard deviation, median, minimum, and maximum) of the maximum, minimum, and last value during the on-treatment period by dose group. Summaries using descriptive statistics of the change from baseline to the maximum, minimum, and last value during the on-treatment period will also be given by dose group.

11.2.5.5 12-Lead Electrocardiograms

ECG intervals will be stratified into categories indicative of potential clinical significance. Each patient’s maximum QT and QT_C intervals from the pre-treatment visit and treatment period visits will be classified as ≤450 msec, >450 to ≤480 msec, >480 to ≤500 msec, and >500 msec. For

each patient's maximum change from the pre-treatment ECG visit for QT and QT_C, intervals will be classified into <30 msec, ≥30 to <60 msec, and ≥60 msec. The number and percentage of patients in each classified category will be presented.

Descriptive statistics will be used to summarize other ECG parameters of PR, QRS, QT, and RR interval, and the corresponding changes from pre-treatment ECG visit at each time point. Plots of the mean QT/QT_C over time for C1D1 and End-of-Study/pre-treatment ECG day measurements will be provided.

11.2.5.6 Other Safety Measurements

Body weight and ECOG performance status will be summarized with descriptive statistics (N, mean, standard deviation, median, minimum, and maximum) and frequencies and percentages for relevant categories. Concomitant medications/procedures will be tabulated and summarized.

11.2.6 Patient Reported Outcomes

PROs will be measured using the FACT-B questionnaire in all patients with both a baseline assessment and at least one post-baseline assessment.

The baseline PRO measurement will be defined as the last value prior to or on the day of the first dose of lucitanib. The on-treatment period will be defined as the day after the first dose of lucitanib to 28 days after the last dose of protocol-specified treatment. PRO measurements collected during the on-treatment period will be included in the summary tables.

The summary of PRO data will include descriptive statistics (N, mean, standard deviation, median, minimum, and maximum) of the maximum, minimum, and last value during the on-treatment period. Summaries using descriptive statistics of the change from baseline to the maximum, minimum, and last value during the on-treatment period will also be given by relevant cohort.

11.2.7 Population PK Analyses

A separate POPPK data analysis plan will be developed and will outline the detailed approach to data handling, model development and diagnostics, individual model parameter estimation, exploration of covariate effects, and final model evaluation techniques. POPPK analyses and results will be reported separately.

11.2.8 Exploratory Analyses

The exploratory endpoints will be summarized descriptively.

11.3 Sample Size Considerations

Up to 200 patients will be enrolled.

A total of at least 80 patients in the 10 mg arm is sufficient to reliably estimate the median PFS and 6 month PFS rate in these heavily pre-treated patients. An observed median PFS greater than 4 months or a 6-month PFS rate of at least 40% will be sufficient to consider the 10 mg dose group worthy of further study. Therefore, with at least 80 patients treated at 10 mg, the width of the 90% confidence interval for the 6 month PFS rate will be less than $\pm 10\%$, so that if the observed 6 month rate is 50% then the lower limit on the confidence interval will be greater than 40%.

The treatment effect in Cohort C (biomarker negative sub-group) is not expected to be as large as in Cohorts A and B; however, the same target of 40% will be used to evaluate Cohort C. With 40 patients, the width of the 90% confidence interval for the 6 month PFS rate will be less than $\pm 15\%$, so that if the observed 6 month rate is less than 25% then the upper limit on the confidence interval will be less than 40%, which is evidence that subsequent studies of 10 mg should exclude biomarker negative patients.

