4.2 Endpoints

4.2.1 Primary Endpoint

- PFS per RECIST Version 1.1 as determined by the investigator

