9.5.2 Efficacy Evaluations

9.5.2.1 Tumor Assessments

The first on-treatment scan should be completed on Cycle 2, Day 1, and every 8 ± 1 weeks through Cycle 6 (i.e., C4D1, C6D1). Thereafter, scans should be completed every 12 ± 1 weeks (i.e., C9D1, C12D1, C15D1, etc.) until disease progression. All patients must have scans to confirm radiographic progression. Tumor scans do not need to be repeated at end-of-study if <2 weeks since last scan or the patient had disease progression at the last scan. Patients that permanently discontinue lucitanib should continue scans until radiographic disease progression. Scans will be evaluated locally for patient treatment decisions. Copies of tumor scans will be

collected centrally to facilitate independent evaluation if subsequently required. Tumor response will be interpreted using RECIST Version 1.1 ([Appendix A](#)).

Tumor assessments should consist of clinical examination and CT scans of the chest, abdomen, and pelvis with intravenous contrast and appropriate slice thickness per RECIST Version 1.1; other alternative studies (MRI and X-ray) may be performed if clinically indicated. The same methods used to detect lesions at baseline are to be used to follow the same lesions throughout the clinical study.

Brain imaging is required at baseline. Patients with brain lesions detected at baseline require repeat brain imaging as part of the follow-up tumor assessments. The same methods used to detect brain lesions at baseline are to be used to follow the lesions throughout the clinical study.

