11.2.4 Efficacy Analyses

Kaplan-Meier methodology will be used to summarize the time to event variables. The 25th, 50th (median), and 75th percentiles will be presented along with the Kaplan-Meier estimates of the 6 and 12 month rates. The efficacy results may be presented separately by cohort or the three cohorts together.

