In some circumstances it may be difficult to distinguish residual disease from normal tissue. When the evaluation of CR depends upon this determination, it is recommended that the residual lesion be investigated (fine needle aspirate/biopsy) before assigning a status of CR. FDG-PET may be used to upgrade a response to a CR in a manner similar to a biopsy in cases where a residual radiographic abnormality is thought to represent fibrosis or scarring. The use of FDG-PET in this circumstance should be prospectively described in the protocol and supported by disease specific medical literature for the indication. However, it must be acknowledged that both approaches may lead to false positive CR due to limitations of FDG-PET and biopsy resolution/sensitivity.

For equivocal findings of progression (e.g., very small and uncertain new lesions; cystic changes or necrosis in existing lesions), treatment may continue until the next scheduled assessment. If at the next scheduled assessment, progression is confirmed, the date of progression should be the earlier date when progression was suspected.

Frequency of tumor re-evaluation

Frequency of tumor re-evaluation while on treatment should be protocol specific and adapted to the type and schedule of treatment. However, in the context of phase 2 studies where the beneficial effect of therapy is not known, follow-up every 6–8 weeks (timed to coincide with the end of a cycle) is reasonable. Smaller or greater time intervals than these could be justified in

specific regimens or circumstances. The protocol should specify which organ sites are to be evaluated at baseline (usually those most likely to be involved with metastatic disease for the tumor type under study) and how often evaluations are repeated.

Normally, all target and non-target sites are evaluated at each assessment. In selected circumstances certain non-target organs may be evaluated less frequently. For example, bone scans (scintigraphy) may need to be repeated only when CR is identified in target disease or when progression in bone is suspected.

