## **4** GENERAL ANALYSIS CONSIDERATIONS

Due to significant changes to the study design throughout the study, all summaries of data will be presented by initial study drug dose level (10 mg, 15 mg) regardless of a patient's enrollment into study cohorts A, B, and C. Initial dose groups will be referred to as treatment groups (10 mg, 15 mg). An overall column combining all patients from both treatment groups will be included in the data summaries, where applicable.

Quantitative variables will be summarized using descriptive statistics (N, mean, standard deviation, median, minimum, and maximum) and/or frequency and percentages for medically relevant categories. Categorical variables will be presented using frequencies and percentages. Exact 95% confidence intervals may be presented for frequencies.

All data will be used to their maximum possible extent but without any imputations for missing data.

All statistical analyses will be conducted with the statistical analysis software (SAS®) System, Version 9.3 or higher.

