## **5** ANALYSIS POPULATIONS

Per Amendment #5 of the protocol, the following analysis populations were defined for the study:

**Efficacy Population** – all patients who have received at least one dose of lucitanib and are confirmed as *FGFR1*-, 11q-amplified, or FGF non-amplified per the central laboratory.

Safety Population – all patients who have received at least one dose of lucitanib.

For the final statistical analyses to be conducted in support of the clinical study report, the **Efficacy Population** is redefined as all patients who have received at least one dose of lucitanib and have at least one post-baseline tumor scan.

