## **12** EFFICACY ANALYSIS

#### **12.1** Primary Efficacy Analysis

Kaplan-Meier methodology will be used to summarize the time to event variables including the estimated 50th (median) percentile by treatment group.

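### Do the 4- and 6-month go cut-offs need a further analysis because they fall between scheduled scans?

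*Protocol*

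**What the plan says.** The primary endpoint (Protocol 4.2.1) is "PFS per RECIST Version 1.1 as determined by the investigator". Protocol 11.3 states the rule, repeated in SAP section 3: "An observed median PFS greater than 4 months or a 6-month PFS rate of at least 40% will be sufficient to consider" the 10 mg group worth further study.

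Protocol 9.5.2.1 puts the first on-treatment scan at Cycle 2 Day 1, then "every 8 ± 1 weeks through Cycle 6 (i.e., C4D1, C6D1). Thereafter, scans should be completed every 12 ± 1 weeks" until progression. Cycles last 28 days.

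Protocol 11.2.4 plans Kaplan-Meier quartiles "presented along with the Kaplan-Meier estimates of the 6 and 12 month rates". SAP 12.1 is shorter: "Kaplan-Meier methodology will be used to summarize the time to event variables including the estimated 50th (median) percentile by treatment group". Neither document plans an interval-censored PFS estimate or a progression-free proportion at a named scan.

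On equivocal findings that are later confirmed, Appendix A says that "the date of progression should be the earlier date when progression was suspected". It moves the date back to an earlier assessment, not to a point between assessments.

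**The concern.** A progression that occurs between two scans is normally dated at the later one. If no scan is due near month 4 or month 6, a Kaplan-Meier curve built on scan dates is nearly flat through both cut-offs. The reported median could then exceed 4 months when the data show only that more than half the patients were progression-free at week 12.

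In a randomised comparison with a common schedule, this delay affects both arms. Here randomisation was removed by Amendment 4, and the rule sets one observed value against a fixed number. What would be at stake is a go decision for a drug whose true median is nearer 3 months than 4, with nothing in the planned output to alert the reader.

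**Working it through.** **1. The plan's own precision figures.** The 90% half-width is 1.645 × √(p(1−p)/n).
- n = 80, p = 0.50: 1.645 × √(0.25/80) = 9.2 points, lower limit 40.8%. This agrees with the stated limit above 40%.
- n = 40, p = 0.25: 1.645 × √(0.1875/40) = 11.3 points, upper limit 36.3%. This agrees with the stated limit below 40%.

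**2. The calendar.** With 30.4375 days per month, 4 months = 121.75 days = week 17.39 and 6 months = 182.63 days = week 26.09. Scans are due at weeks 4, 12, 20 and 32. Let every window accumulate: ±2 days (0.29 week) at Cycle 2 Day 1, then ±1 week per interval.
- Week 12 ± 1.29: 10.7 to 13.3
- Week 20 ± 2.29: 17.7 to 22.3
- Week 32 ± 3.29: 28.7 to 35.3

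Neither cut-off falls in a window. In the PK sub-study (up to 20 patients) the first dose is at Day −7, so scans come at least a week later on the PFS clock. A 1-week shift changes nothing. It would take a gap of 26.09 − 22.29 = 3.8 weeks for even the latest week-20 scan to reach 6 months.

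**3. Every event dated at a scheduled scan.** Assume exponential times with true median m, S(t) = 2^(−t/m), n = 80 and no dropout. The median clause needs at least 41 of 80 event-free at 4 months; the 6-month clause needs at least 32 of 80. Scan dating replaces S(4 months) by S(12 weeks = 2.76 months) and S(6 months) by S(20 weeks = 4.60 months).

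| True median (months) | S(12 wk) / S(4 mo) | Median clause: scan / exact | 6-month clause: scan / exact |
|---|---|---|---|
| 3.0 | 0.529 / 0.397 | 66% / 2% | 18% / 0.2% |
| 3.5 | 0.579 / 0.453 | 91% / 17% | 56% / 4% |
| 4.0 | 0.620 / 0.500 | 98% / 46% | 85% / 23% |

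**4. Some events dated between scheduled scans.** Deaths, unscheduled scans, clinical findings and End-of-Study scans do this. The documents give no share f, so f = 10/30/50/70% is an assumption.
- Break-even true median, from (1−f)·S(12 weeks) + f·S(4 months) = 0.5: 2.87/3.10/3.34/3.60 months.
- Simulated chance of passing the whole rule at m = 3.0: 57/39/22/11%, against about 2.5% with exact dating. A different convention when exactly half are event-free gives 59/42/26/13%, against 3%.
- Trials in which week-12 status gives the same answer as the median clause (m = 3.0): 91–93% at f = 10%, 72–78% at 30%, 56–68% at 50% and 44–62% at 70%. The spread comes mainly from reading status at each patient's own scan or just after the scan window.

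So the claim that the median clause is really a week-12 test holds when few events fall between scans and fails when most do.

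**5. Would the obvious remedy help?** Take a Weibull interval-censored fit (last clear scan to first progression scan, scheduled or not; deaths exact), with a required statement that the result depends on scan timing whenever Kaplan-Meier meets the rule and the fit does not. At a true median of 4.5 months, above the cut-off, that statement appears as follows for f = 10/30/50/70%:
- If the between-scan events are unscheduled scans taken at progression: 19–23/33/43–47/45–49% of trials.
- If they are all exactly dated, as deaths are: 11–21% across the range.

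The first case is biased because a scan prompted by symptoms falls close to the progression itself, yet the fit spreads that event back to the previous clear scan and places it too early.

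**The case for a change.** The strongest case for a change is that the calendar fact needs no model and that there is no concurrent control to absorb the delay. The two clauses are joined by *or*, and no confidence bound on the median is required. Even with 70% of events dated between scans, the pass rate at a true median of 3.0 months is about four times that with exact dating (11% against 2.5%). SAP 12.1 names only the median, so even the 6-month rate is no longer listed there. Reporting progression-free proportions at weeks 12 and 20 would need no model and no new data.

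The calendar fact stands. So does the point that the disease control rate is only a partial counterpart: it requires stable disease for at least 12 weeks but counts a response even if it was lost by then, and it is not tied to the rule.

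The rest does not amount to a needed change. The leniency is measured against a quantity the plan does not claim to estimate. If 4 months and 40% came from trials scanned on a similar schedule, the benchmarks carry the same delay and some or most of the effect cancels. The documents give no source, so net leniency is neither shown nor excluded. The week-12 and week-20 proportions are points on a curve already planned, and they alter neither the estimate nor the decision. SAP 12.1 does not exclude the 6-month rate, which Protocol 11.2.4 plans and SAP section 3 keeps in the rule.

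**Conclusion.** No change is needed. Both cut-offs do fall between scheduled scans, and for scan-dated progressions the median clause reflects week 12 and the 6-month rate week 20. That is an ordinary property of RECIST PFS. The rule is worded for an observed value, Kaplan-Meier on assessment dates estimates the endpoint as defined, and the plan's precision figures are correct.

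The gap from the unseen progression time could be sizeable: the break-even true median is 2.9 to 3.6 months for a nominal 4. That range rests on an assumed 10–70% of events dated between scans; the pass rates also assume exponential times and no dropout. It says nothing about leniency relative to benchmarks that may have been obtained in the same way.

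An interval-censored fit with a compulsory caveat is a poor trade: it would question the result in roughly a fifth to a half of trials of a drug whose true median is 4.5 months, if the between-scan events are symptom-prompted scans. Scan-time proportions are harmless and an analyst may quote them from the Kaplan-Meier curve, but nothing in the plan depends on them.

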
Statistical Procedures
	
Analysis Populations
 
 • Efficacy population: all treated patients who received at least one dose of lucitanib and are confirmed as FGFR1- or 11q-amplified per the central laboratory • Safety population: all patients who have received at least one dose of lucitanib 
Sample Size Justification
 
Approximately 200 patients will be enrolled to the 10 mg and 15 mg daily dosing groups. A total of at least 80 patients in the 10 mg arm is sufficient to reliably estimate the median PFS and 6 month PFS rate in these heavily pre-treated patients. An observed median PFS greater than 4 months or similarly a 6-month PFS rate of at least 40% will be sufficient to consider the 10 mg dose group worthy of further study. Therefore, with at least 80 patients treated at 10 mg, the width of the 90% confidence interval for the 6 month PFS rate will be less than $\pm 10\%$ so that if the observed 6 month rate is 50% then the lower limit on the confidence interval will be greater than 40%.
 
Cohort C will enroll up to 40 patients to evaluate whether the PFS of a FGF non-amplified population is comparable to patients who are FGFR1- or 11q-amplified (Cohorts A and B).
 
The same target response of 40% will be used to evaluate Cohort C. With 40 patients, the width of the 90% confidence interval for the 6 month PFS rate will be less than $\pm 15\%$, so that if the observed 6 month rate is less than 25% then the upper limit on the confidence interval will be less than 40%, which is evidence that subsequent studies of 10 mg should exclude FGF non-amplified patients.
 
Statistical Methods
 
The Kaplan-Meier methodology will be used to summarize the primary endpoint of PFS. The 25th, 50th (median), and 75th percentiles will be presented along with the Kaplan-Meier estimates of the 6 and 12 month PFS rates.
 
The ORR and DCR will be summarized with frequencies and percentages. The DR and OS will be summarized utilizing Kaplan-Meier methodology.

Data Monitoring Committee
	
A data monitoring committee (DMC) consisting of two external investigator advisors and specified Clovis personnel will meet approximately quarterly after the first patient is enrolled to review the efficacy and safety data.
 
A detailed description of the composition, roles and responsibilities, and functioning of the DMC is provided in the DMC Charter.

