5 STUDY DESIGN

5.1 Overall Study Design and Plan

This is a phase 2, open-label, multicenter study evaluating the efficacy and safety of lucitanib administered orally to patients with metastatic breast cancer. Patients with *FGFR1*- or 11q (FGF3, FGF4, Cyclin D1, or FGF19)-amplified metastatic breast cancer may be enrolled into one of two different cohorts (Cohort A: FGF-amplified or Cohort C: FGF non-amplified, both receiving 10 mg daily).

For patients with local *FGFR1* or 11q test results, a central laboratory will confirm the presence or absence of the *FGFR1* and/or 11q amplification. Central testing prior to enrollment for these patients is not required for study enrollment.

Patients with local *FGFR1* and 11q results for whom the central reading does not confirm the amplification status can continue the study at the discretion of the investigator if clinical benefit is observed. If there are a significant number of patients with discordant local and central testing results, additional patients may be enrolled.

For patients without a local *FGFR1* or 11q test result, tissue may be submitted for central testing under a prescreening process, and a positive central laboratory test result is required for screening and subsequent enrollment of these patients.

FGFR1-amplified and 11q-amplified patients will be enrolled* as follows:

- Cohort A (10 mg): approximately 80 patients

FGF non-amplified patients will be enrolled as follows:

- Cohort C (10 mg): up to 40 patients

The dose assigned to patients enrolled into Cohort C depends on the version of the amendment approved at the time of patient enrollment (Amendment #3: 15 mg; Amendment #4: 10 mg).

*Amendment #4 removes the 1:1 randomized treatment assignment (10 mg vs. 15 mg) and accrual of patients to Cohort B (15 mg). Up to 80 patients were expected enrolled into Cohort B under the previous versions of this protocol.

Up to 20 patients enrolled will participate in a PK sub-study to assess the comparative PK of the lucitanib tablet formulation taken at Day -7 with the lucitanib capsule formulation taken at Day 1.

Patients in Cohorts A or C will be enrolled in the PK sub study at participating sites, as follows:

- Participation in the PK sub study will be optional for patients participating in Cohort A
- Participation in the PK sub study will be required for patients participating in Cohort C until enrollment of the PK sub study is completed

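### The only Cohort C criterion tests non-amplified patients against a fixed 40%: it can show low activity but not comparability with amplified patients, and the SAP does not carry forward the FGF comparison that the protocol plans.

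*Protocol*

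**What the plan says.** The synopsis (Sample Size Justification) says that Cohort C enrols up to 40 patients "to evaluate whether the PFS of a FGF non-amplified population is comparable to patients who are" *FGFR1*- or 11q-amplified, meaning Cohorts A and B.

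Protocol 11.3 expects a smaller effect in Cohort C but says that "the same target of 40% will be used to evaluate Cohort C". It continues: "With 40 patients, the width of the 90% confidence interval for the 6 month PFS rate will be less than" ±15 points, and "if the observed 6 month rate is less than 25% then the upper limit on the confidence interval will be less than 40" per cent, "which is evidence that subsequent studies of 10 mg should exclude biomarker negative patients". SAP 3 repeats this.

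The same section has a companion criterion for the 10 mg group, with at least 80 patients: an observed median PFS above 4 months, or a 6-month rate of at least 40%, is enough to take that dose further.

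Protocol 11.2.1 says the *FGFR1*-amplified, 11q-amplified and non-amplified subgroups will be compared among patients initially treated at 10 mg, and again over both doses. It gives no estimator, interval or link to a decision. Protocol 11.2.4 lists 6- and 12-month Kaplan-Meier rates and allows presentation by cohort.

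SAP 4 presents all summaries by initial dose, whatever the cohort. SAP 12.1 names only the median, by treatment group.

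On dose, Protocol 5.1 says: "The dose assigned to patients enrolled into Cohort C depends on the version of the amendment approved at the time of patient enrollment", namely 15 mg under Amendment #3 and 10 mg under Amendment #4.

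**The concern.** The stated question is relative: do non-amplified patients do about as well as amplified patients? The criterion is absolute: is Cohort C below 40%? The conclusion is about patient selection by FGF status, which is relative again. A low Cohort C rate may mean that FGF status matters, or that the drug does little in either group. A Cohort C rate near 40% is compatible with amplified patients doing the same or much better. The criterion cannot tell these cases apart.

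The comparison in Protocol 11.2.1 would help, but an analyst following the SAP as written would produce neither the Cohort C 6-month rate, which the criterion needs, nor an FGF contrast. The criterion in SAP 3 therefore has no matching analysis in SAP 12.

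The conclusion is also worded for 10 mg, while some of the 40 may have started at 15 mg. At stake is how well supported a recommendation on FGF selection in later studies would be.

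**Working it through.** **Inputs.** Cohort C n = 40, two-sided 90% CI, target 40%, trigger an observed rate below 25%, 10 mg group n = 80 (Protocol 11.3, SAP 3). True rates below are assumptions. All patients are taken as evaluable at 6 months; earlier censoring would widen every interval.

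**1. The plan's own figures.** Half-width = 1.645 × √(p(1−p)/n).
- n = 40, p = 0.25: 1.645 × √(0.1875/40) = 0.113, upper limit 36.3% (Clopper-Pearson 38.7%).
- n = 40, p = 0.50 (widest case): 1.645 × √(0.25/40) = 0.130.
- n = 80, p = 0.50: 1.645 × √(0.25/80) = 0.092, lower limit 40.8% (Clopper-Pearson 40.3%).

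All stated properties reproduce.

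**2. What the criterion responds to.** Below 25% of 40 means at most 9 patients. The exact binomial P(X ≤ 9 | 40, p) is:

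| True Cohort C rate | 20% | 25% | 30% | 40% |
|---|---|---|---|---|
| Criterion met | 73% | 44% | 20% | 1.6% |

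The amplified rate does not appear in the calculation. If the trigger is read as an upper limit below 40%, it reaches 11 of 40 (Wald limit 39.1%), and the values at 25%, 30% and 40% become 72%, 44% and 7%.

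**3. Adding the companion criterion.** The damaging outcome is that amplified patients go forward while equally responsive non-amplified patients are excluded. Let 80 amplified patients have to reach at least 32 of 80 (40%) at 6 months.
- Both groups truly 25%: 0.0022 × 0.44 = 0.1%.
- Both truly 30%: 0.036 × 0.196 = 0.7%.

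If a median above 4 months also suffices (exponential PFS, no censoring), amplified patients pass in about 2.4 to 3% and 15 to 18% of trials, depending on how the sample median is taken. The joint probabilities are then about 1% and 3 to 3.5%.

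**4. What a direct contrast would give.** For 80 versus 40, half-width = 1.645 × √(pA(1−pA)/80 + pC(1−pC)/40).
- 20% v 20%: 12.7 points. 40% v 25%: 14.4. 50% v 25%: 14.5. 60% v 40%: 15.6.
- The 90% CI lies wholly above zero in about 86% of trials at 50% v 25%, 68% at 60% v 40%, and 6% when both rates are 25% or 30%.

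**5. 15 mg starters.** Their number is not given. Counting 10 mg starters only:
- An upper limit below 40% at an observed 25% needs n > 1.645² × 0.1875/0.15² = 22.5, so at least 23 (n = 22 gives 40.2%). It fails if 18 or more of the 40 started at 15 mg.
- A half-width below 15 points at every rate needs n > 1.645² × 0.25/0.15² = 30.1, so at least 31. It fails if 10 or more started at 15 mg.

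If the 15 mg starters stay in, the result depends on the mix. With true rates of 20% at 10 mg and 40% at 15 mg, the criterion is met in 73%, 44% and 19% of trials with 0, 10 and 20 such patients. With 30% and 10%, it is met in 20%, 44% and 74%.

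**The case against.** The strongest case on the other side has five parts.

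- **A comparison is planned.** A reader might infer that the trial contains no FGF contrast. Protocol 11.2.1 rules that out: it plans one, in 10 mg starters. What remains is that it has no method or role in the conclusion and is missing from the SAP.
- **The 44% is not a rate of harmful error.** A reader might take 44% (or 73%) as the chance of wrongly singling out non-amplified patients. If both groups are that poor, the 10 mg group seldom meets its own criterion, and step 3 brings the joint risk to between 0.1% and about 3.5% at true rates of 25% to 30%. This stands.
- **60% versus 40% is not a failure of the rule.** A true 40% in Cohort C is the protocol's own target, so not excluding those patients is consistent with it. This stands too, although comparability would still be unanswered.
- **Dose mixing is a possibility, not a fact.** The enrolment sections label Cohort C as 10 mg, up to 40, and SAP 4 separates starting doses. The total of 200 equals 80 + 80 + 40, which leaves no separate allowance for 15 mg Cohort C patients, but Cohort B closed early, so this does not settle it.
- **The comparability purpose is stated only in the synopsis.** The formal objectives contain no such comparison. That limits the weight of the point, but 11.2.1 shows that the contrast is intended.

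**Conclusion.** The criterion is sound as a low-activity screen and does not answer the comparability question. On its own it does not support a conclusion about selecting patients by FGF status. The SAP widens the gap, because it calls for neither the 6-month rate in non-amplified patients nor the comparison in Protocol 11.2.1.

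The chance of advancing amplified patients while wrongly excluding equally responsive non-amplified patients is small: about 1% at a common true rate of 25% and 3 to 3.5% at 30%, under exponential PFS without censoring. The main cost is a stated question left unanswered, with a biomarker conclusion attached to a result that has no FGF contrast.

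The documents do not show how many Cohort C patients started at 15 mg, so the thresholds of 23 and 31 are conditions to check and not demonstrated failures. The change is worth making because it is cheap and uses data already collected.

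**What to change.** In Protocol 11.3 and SAP 3, with the matching analysis in SAP 12.1:

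- **(a)** Apply the 40% criterion to non-amplified patients who started at 10 mg, state how many there are, and restate the half-width for that number.
- **(b)** Report 6-month Kaplan-Meier PFS by FGF status in 10 mg starters, and the amplified-minus-non-amplified difference with its 90% CI. This implements Protocol 11.2.1.
- **(c)** Describe the 40% criterion as evidence of insufficient activity in non-amplified patients, and read any conclusion about FGF selection alongside the difference in (b).

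A CI excluding zero should not be the sole trigger for exclusion. At 60% v 40% it would exclude a group that meets the 40% target in about 68% of trials. At 35% v 20% it would exclude a low-activity group in about 57%, against 73% under the present criterion.

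The cost is a few sentences and one added estimate. FGF status is already a baseline variable in SAP 8.2, and no patients or visits are added. There are two limits. The difference is imprecise, at about ±13 to 16 points with 80 versus 40, and wider with fewer 10 mg starters. Without a control arm it cannot separate a predictive from a prognostic effect, and Protocol 3.2 itself links 11q amplification to poor prognosis.
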